Methods: This pilot randomized controlled trial intends to include 30 stable COPD patients, who are psychologically distressed and will be randomly assigned to the intervention (appbased mindfulness + treatment as usual) and waitlist control (treatment as usual) condition. The intervention group will be introduced to the intervention in a face-to-face learning phase (single day) conducted by the study coordinator while being hospitalized. Patients in the intervention group will be instructed to practice mindfulness daily using at least one of 4 short exercises (10-15 minutes) over a period of 8 weeks, starting in the hospital and continuing at home. The exercises will be delivered by a software (movisensXS). Additionally, dyspnoea, stress, relaxation, affect and oxygen saturation (assessed by a pulse oximeter) will be assessed before and after each exercise via the software.

Questionnaire data will be collected equally in both groups at 5 measurements: baseline, after 4 weeks, after the intervention (8 weeks) and at follow-up (4 and 6 months). Physiological measures (heart rate variability, electrodermal activity, heart rate) will be conducted at the same 5 measurements, using an ecg and eda sensor (movisens EcgMove4, movisens EdaMove4). Physiological measures will be assessed during the conduction of a cognitive stress test (Stroop-test), as well as before and after the conduction (at rest). Hair cortisol will be collected at baseline, after the intervention (8 weeks) and at follow-up (4 and 6 months). Face-to-face exit interviews will be conducted in the intervention group after 8 weeks to further assess patients' experiences with the intervention.

The primary outcome measures are psychological distress and the intervention's feasibility. The secondary outcome parameters for immediate effects of mindfulness exercises will be dyspnoea, stress, relaxation, affect (anxiety, depression, happiness) and oxygen saturation. The secondary outcome parameters for intermediate and long-term effects are heart rate variability, electrodermal activity, heart rate, health-related quality of life, health status impairment, fatigue, breathlessness catastrophizing, perceived and chronic stress, mindfulness and self-compassion. Additionally, compliance regarding medication-intake, perception of exacerbations, frequency and intensity of exacerbations and hospitalization rate as well as patients' experiences with the intervention are assessed.

Klinik Ottakring

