INCLUSION CRITERIA	 spirometry confirmed (FEV1 <80%) COPD diagnosis psychological distress (as assessed by the Hospital Anxiety and Depression Scale): HADS-A ≥ 8 OR HADS-D ≥ 8 OR HADS total score ≥ 16 age ≥ 40 years ability to understand German physical and mental capability to attend the intervention, judged by the treating physician life expectancy > 6 months as judged by treating physician ability to use a smartphone
EXCLUSION CRITERIA	 ability to use a smartphone auditory impairment active asthma diagnosis any other known severe comorbidities such as heart failure (LVF<35%), uncontrolled diabetes, concomitant cancer, stroke, unstable coronary heart disease, respiratory failure history of/current severe psychological disorder (e.g. schizophrenia, severe cognitive impairment) current acute exacerbation of COPD any other relevant acute health crisis interfering with the study intervention (e.g. Covid-19) receiving any psychosocial treatment (e.g. psychotherapy) regular other systematic mind-body-practice
STUDY PERIODS	Period 1: individual mindfulness practice at home (baseline - 8 weeks)
	Period 2: Follow-up (3 months and 6 months)

VV

Wiener Gesundheitsverbund Klinik Floridsdorf

MEASUREMENTS	Paper-pencil data collection (baseline, 4 weeks, 8 weeks, 4 months, 6 months) psychological distress, perceived stress, health related quality of life, health status impairment, fatigue, mindfulness, self-compassion, breathlessness catastrophizing
	Psychophysiological data collection (baseline, 4 weeks, 8 weeks, 4 months, 6 months): heart rate variability, electrodermal activity (before, during and after the conduction of a cognitive task (Stroop-test))
	EMA data collection (daily for intervention period of 8 weeks):
	 pre-meditation (event-based): dyspnea, acute perceived stress, relaxation anxiety, depression, happiness, oxygen saturation (pulse oximeter) post-meditation (event-based): dyspnea, acute perceived stress, relaxation anxiety, depression, happiness, oxygen saturation (pulse oximeter)
STUDY TIME-LINE	Recruitment:
	 pulmonary ambulances of the Klinik Ottakring and Klinik Floridsdorf previously hospitalized COPD patients in the Klinik Ottakring and Klinil Floridsdorf invitation to the intervention via telephone call or personal invitation in the pulmonary ambulance (flyer and oral information)
	• invitation to the intervention via posting a flyer on social media (Facebook)
	Telephone-Screening:
	screening for inclusion and exclusion criteria

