PRIMARY	Feasibility (exit interview, drop-out-rate)
OUTCOME VARIABLES	Intermediate and long-term effects of daily mindfulness practice:
VANIADLES	• Psychological distress (Hospital Anxiety and Depression Scale)
SECONDARY OUTCOME	 Immediate effects of mindfulness exercises: Acute perceived stress (visual analogue scale)
VARIABLES	Dyspnea (Borg Dyspnea Scale) Delayation (Likert and a MDRE)
	 Relaxation (Likert scale based on MDBF) Affect (anxiety, depression, happiness; based on HADS) Overgen seturation in blood (Bules Ovimeter)
	Oxygen saturation in blood (Pulse Oximeter)

	Intermediate and long-term effects of daily mindfulness practice:
	 Heart rate variability, heart rate (chest belt) Electrodermal activity (EDA-sensors) Chronic stress (hair-cortisol) Chronic stress (Perceived Stress Scale) Health related quality of life (Chronic Respiratory Questionnaire) Health status impairment (COPD-Assessment Test) Fatigue (Multidimensional Fatigue Inventory) Mindfulness (German Version of Freiburg Mindfulness Inventory – Freiburger Fragebogen zur Achtsamkeit) Self-compassion (Self Compassion Scale) Breathlessness Catastrophizing (Breathlessness Catastrophizing Scale) Further outcomes: Compliance regarding medication Perception of exacerbations (exit interview)
	Hospitalization rateFrequency and intensity of exacerbations
STATISTICAL METHODOLOGY	Primary hypotheses: It is hypothesized that the digital MBI will be feasible in the ambulant setting. Furthermore, it is assumed that the digital intervention will reduce psychological
	distress. The feasibility of the study will be examined using descriptive analyses, looking deeper into drop-out-rates, recruitment, adherence and patients' personal factors.
	Statistical analyses:
	Groups (intervention vs. waitlist) will be compared regarding subjective variables (e.g. psychological distress), biological variables (hair cortisol levels), and physiological responses of the autonomous nervous system (heart rate variability, electrodermal activity) to the mental stressor using analyses of variance (ANOVAs) with repeated measurement. These analyses test for main effects of time (within subject factor) and group (between subject factor) as well as their interaction effect. In case the requirements of ANOVAs are not met, a non-parametric pendant will be used. Furthermore, mediating (e.g. mindfulness) and moderating (e.g. age, gender, disease severity) effects will be analysed.

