	For the analysis of the EMA data in the intervention group, multilevel modelling will be used to fit the nested data structure. A two-level model (level 1 = within persons, level 2 = between persons) will be used, with all the assessed subjective variables (e.g. momentary stress) nested on level 1 due to multiple measurements. Pre-post effects of the assessed subjective variables will examine the immediate effects of the MBI.
	Telephone exit interviews will be recorded and analysed using thematic analysis and a mixed methods approach.
DATA	Paper-pencil-data:
MANAGEMENT	• Digitalization: As data are collected on different sites by student research assistants, data will firstly be transported to the Department of Clinical and Health Psychology, University of Vienna, Austria. There, data will be digitalized.

For this process, data will be safely stored in a locked cupboard in the Department of Clinical and Health Psychology, University of Vienna, Austria. Only members of the research team have access to the key.

Klinik Floridsdort

- Final storage of physical data: The study coordinator will transport the physical data safely to the Klinik Ottakring, Vienna, Austria, where the data is finally stored in a locked cupboard. Only members of the research team have access to the key.
- Storage of digital data: Digital data will be stored on the share server of the research team led by [name] [name] (University of Vienna, Austria). A project folder "39 SPIROMIND" was created for the data storage. Each person's access to the folder must be approved by [name] [name] and must be activated by the department's IT team. Only members of the SPIROMIND research team have access to the folder. Additionally, data will be stored on the study coordinator's server of the Klinik Ottakring, Vienna, Austria, and on the study coordinator's server of the Department of Clinical and Health Psychology, University of Vienna, Austria.
- Analysis: Data will be analysed using the software IBM SPSS Statistics, version 24, and the software R, version 3.4.2.

EMA data:

- Access to data: Data are stored on the study's private account of the software MovisensXS. Only members of the research team have access to the account.

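### Repeated-measures ANOVA for HADS over a five-visit schedule uses only patients seen at every visit, so a late withdrawal also removes observed 4- and 8-week values from the group comparison

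*Protocol*

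**What the plan says.** The Statistical Methodology section of the protocol names one model for the group comparisons. Subjective variables (psychological distress is the example given), hair cortisol, and heart rate variability and electrodermal activity are compared between arms "using analyses of variance (ANOVAs) with repeated measurement". On the terms it states: "These analyses test for main effects of time (within subject factor) and group (between subject factor) as well as their interaction effect". It does not list the levels of time.

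The schedule supplies them. The Methods part of the Executive Summary says: "Questionnaire data will be collected equally in both groups at 5 measurements". Those measurements are baseline, 4 weeks, 8 weeks, 4 months and 6 months. The Measurements section gives the same five for questionnaires and for psychophysiology.

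The only fallback is for failed model assumptions: "In case the requirements of ANOVAs are not met, a non-parametric pendant will be used". For the app data of the intervention arm a different model is chosen: "multilevel modelling will be used to fit the nested data structure". Drop-out rate is listed with feasibility under Primary Outcome Variables. The sample is 30 patients, 15 per arm. The Data Management section names SPSS and R for the questionnaire data.

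**The concern.** Classical repeated-measures ANOVA works on complete rows. As run by the standard SPSS procedure, a patient who lacks one level of the time factor leaves the whole analysis, including every effect estimated at the visits that patient did attend. With five levels reaching to 6 months, someone who completes the 8-week intervention and its assessment but is missing at month 6 contributes nothing to the time-by-group test.

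Two things are at stake. Data already collected on a primary outcome are thrown away in a sample of only 30. And the comparison is then between patients who completed every visit, not between the groups as randomised. The protocol treats drop-out as a question to be measured, so incomplete rows are foreseeable. It also already plans a model class that tolerates them, but only for the app data.

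**Working it through.** The protocol states no drop-out rate, SD, correlation, effect size or power, so there is no figure of its own to reproduce. What follows shows the consequence under stated assumptions.

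**Inputs from the protocol:** N = 30 (15 per arm); five questionnaire visits, hence four after baseline; week 8 is the second of those four.

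**Assumed:** a proportion p of those remaining withdraws at each post-baseline visit and does not return.

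**Step 1. Observed patients lost.**
- Complete at all five visits: 30 × (1 − p)^4
- With an 8-week value: 30 × (1 − p)^2

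| p | complete at all visits | with 8-week data | discarded although observed at 8 weeks |
|---|---|---|---|
| 5% | 30 × 0.8145 = 24.4 | 30 × 0.9025 = 27.1 | 2.6, about 3 |
| 10% | 30 × 0.6561 = 19.7 | 30 × 0.8100 = 24.3 | 4.6, about 5 |
| 15% | 30 × 0.5220 = 15.7 | 30 × 0.7225 = 21.7 | 6.0, about 6 |

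**Step 2. Precision.** With loss unrelated to outcome, the standard error of a simple 8-week change contrast is proportional to 1/√n. Using completers instead of everyone seen at week 8 inflates it by √[(1 − p)^2 / (1 − p)^4] = 1/(1 − p), that is by about 5%, 11% and 18%. This ratio does not depend on the SD.

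**Step 3. Bias.** Assumed: HADS total SD 6, correlation 0.6 between baseline and week 8, no true effect, and 20%, 30% or 40% of each arm leaving after week 8. The SD of change is then 6 × √(2 × 0.4) = 5.4. Where leaving depends on outcome, the odds of leaving double per SD of less improvement. Completers' difference in change from baseline, intervention minus waitlist (negative means apparent benefit):

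| who leaves | 20% | 30% | 40% |
|---|---|---|---|
| intervention arm: those who improve less; waitlist: at random | −0.7 | −1.0 | −1.35 |
| the same dependence in both arms | about 0 | about 0 | about 0 |
| waitlist arm: those who improve less; intervention: at random | +0.7 | +1.0 | +1.3 |

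If instead the intervention patients who improve are the ones who leave, the figure is again positive, about +0.7 to +1.35. On raw 8-week scores rather than change, the first row is about half as large (−0.35 to −0.67). The change scale is the one that matches a time-by-group test.

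**Step 4. Other outcomes.** Heart rate variability and electrodermal activity follow the same five visits, so the same deletion applies. Hair cortisol has fewer samples (four in the Executive Summary, three in the Study Time-line), so the deletion runs over fewer levels.

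**The case against.** **The five levels of time are inferred.** This is correct. One ANOVA to week 8 and a second, longer one would also fit the text, and under that plan a withdrawal after week 8 would not cost the 8-week data. Five levels is still the natural reading of a single time factor set against this schedule. Even a split analysis would drop a patient who missed week 4, or who missed any visit in the longer model.

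**An unseen SAP might impute.** It might, and the absence of a missing-data rule is not the point here. The point is the model that this document fixes for a primary outcome. An SAP that specified a mixed model instead would depart from it.

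**R is named alongside SPSS, and no non-parametric test is named.** Both are true. A reader might infer that the fallback is a Friedman-type test that also needs complete rows; the protocol does not say so, and nothing here rests on it. The complete-row requirement comes from the classical method rather than from one package.

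**A reader might infer that the HADS effect will be biased towards benefit**, because patients who find the exercises unhelpful would leave the intervention arm. The protocol gives no drop-out mechanism, and the sign in Step 3 follows entirely from the one assumed. The documents do not support that inference.

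**A reader might also extend the point to every outcome, or to patients who stop using the app.** Hospitalisation, exacerbations and medication compliance are not in the ANOVA sentence, and nothing in the protocol says that patients who stop the app leave the scheduled visits.

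**This is a pilot.** No confirmatory claim rests on the HADS test. That limits the weight of the point. It does not remove it, since HADS is a primary outcome and the results are meant to inform larger trials.

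**Conclusion.** The point holds for HADS and the other questionnaires, for the psychophysiological measures, and over fewer samples for hair cortisol. On the natural reading of the schedule, the stated ANOVA discards patients whose 8-week values were observed: about 3, 5 or 6 of 30 at assumed withdrawal of 5%, 10% or 15% per visit. Where drop-out is unrelated to outcome, or related to it equally in both arms, the cost is mainly precision. Where it is related differently in the two arms, bias is added: roughly 0.7 to 1.35 HADS points of change in either direction for 20% to 40% loss, assuming SD 6, correlation 0.6 and odds doubling per SD of change. The direction cannot be known in advance. The drop-out rates, SD, correlation and mechanism are all assumptions, since the protocol gives none. The change is worth making because the present choice is stated, a better one is available, and switching is cheap.

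**What to change.** In Statistical Methodology, replace the repeated-measures ANOVA for the group comparisons over visits with a linear mixed model for repeated measures, with visit, group and visit-by-group as fixed effects. State that it uses all observed values of randomised patients in their assigned arm. Keep the complete-case ANOVA as a sensitivity analysis at most.

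The cost is about one sentence. R is already named for these data, and multilevel modelling is already planned for the app data. There are two limitations. The model assumes that missingness is explained by the observed values, and with 30 patients the covariance structure must be kept simple.

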Analysis: This study will realize a mixed methods analysis. Differences between conditions as well as moderating and mediating effects will be calculated. The intermediate pre-post effects of mindfulness exercises will be analysed using multi-level analyses (HLM). Interview data will be analysed using thematic analysis.

Klinik Floridsdorf

Fakultät für Psychologie

Discussion: The study aims to assess the feasibility of a brief app-based mindfulness intervention for stable COPD patients who are psychologically distressed and intends to investigate its effects on psychological distress and various other psychological, psychophysiological and respiratory variables. The results of this study could serve as basis for following large-scale RCTs and advance the future implementation of app-based MBIs as add-on treatment in the clinical practice.

Ethics: The study will be conducted in accordance with the Declaration of Helsinki. It will be asked for examination and agreement by the ethics committee of the city of Vienna. Ethics approval for a similar study for COPD patients following acute exacerbations has already been obtained by the ethics committee of the city of Vienna (serial number EK 20-177-VK).

SPONSOR, INVESTIGATOR, MONITOR AND SIGNATURES

Klinik Floridsdorf

Sponsor/or representative (OEL) (AMG §§ 2a, 31, 32)

Karl-Landsteiner-Institut für Lungenforschung und Pneumologische Onkologie

Signature (OEL)

Investigators (AMG §§ 2a, 35, 36)

Prim. Priv.-Doz. [name], Klinik Ottakring, Vienna, Austria (principal investigator)

Signature

Univ.-[name]. [name], Department of Clinical and Health Psychology, University of Vienna, Austria

Signature

[name], Klinik Ottakring, Vienna, Austria

Signature

[name], B.Sc., Department of Clinical and Health Psychology, University of Vienna, Austria (study coordinator)

Signature

Date

Date

Date

Fakultät für Psychologi

Date

Date

Klinik Floridsdorf

Monitor/ or Representative of CRO (AMG §§ 2a, 33, 34)

Medizinische Universität Wien KKS - Koordinationszentrum für Klinische Studien [name]

Signature

Date

Clinical Trials Centres:

2.Medizinische Abteilung mit Pneumologie, Klinik Ottakring, Vienna, Austria Abteilung für Innere Medizin und Pneumologie, Klinik Floridsdorf, Vienna, Austria

Associated Departments:

Department of Clinical and Health Psychology, University of Vienna, Austria

Wiener Gesundheitsverbund Klinik Floridsdorf

Fü

CLINICAL STUDY PROTOCOL

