	 How often do patients meditate by using the app? How long? When? Do they prefer a specific mindfulness exercise?
	• Which patients benefit the most from the intervention (moderating factors, e.g.
	 age)? Do mindfulness and self-compassion mediate the intermediate and long-term effects on psychological distress?
DESIGN / PHASE	 pilot and feasibility study randomized controlled trial including follow-up
	• two treatment arms: intervention + treatment as usual (TAU) vs. waitlist (TAU)
	 ecological momentary assessment (EMA) study ecological momentary intervention (EMI) study (app-based)
	 prospective and experimental
	mixed methods analysismulti-centred
	multi-centred
STUDY PLANNED DURATION	6 months (8 weeks intervention + follow-up)
CENTER(S)/	Respiratory unit of the "Klinik Ottakring", Vienna, Austria
COUNTRY(IES)	Respiratory unit of the "Klinik Floridsdorf", Vienna, Austria
PATIENTS /	Groups:
GROUPS	 Intervention group: mindfulness exercises + TAU Waitlist control group: TAU
	Sample size: 30 COPD patients (15 patients in each group)
L	

V

Wiener Gesundheitsverbund Klinik Floridsdorf

	Sampling method: screening of all eligible patients during survey period, inclusion of all eligible interested patients
	Blinding: single blinding (of assessors)
	Allocation: equal treatment allocation via block randomization
ETHICS	 patients' written informed consent pseudonymisation of patients: Patients' personal data is noted on 2 documents: the patients' information (name, birth date, code) and the patients' contact details (name, birth date, address, phone number, email address, code). These documents are safely stored in a locked cupboard in the Klinik Ottakring, Vienna, Austria. Only members of the research team have access to the cupboard's key. After the screening, the patient is given a unique reference code (continuous numerical code starting from 01). In the following, only this numerical code will be used to allocate the data to the patient. The allocation of the patients' personal data to their numerical code will only be possible using either the patients' information or the patients' contact details. pseudonymised data analysis provision of mindfulness intervention to waitlist control group after study completion examination and agreement by the ethics committee of the "Wiener Krankenanstaltenverbund", Vienna, Austria

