	Period 1 (patients' home)
	 Day 0: Informed consent Baseline data collection Sociodemographic and medical data Paper-pencil data collection Chronic stress (collection of hair sample) Psychophysiological data collection
	Day 1:
	 Introductory and learning phase (face-to-face) Installation and testing of app, explanation of intervention, conduction of al mindfulness exercises in the presence of study investigator From now on: Individual daily meditation + daily EMA data collection Possibility of consulting the study coordinator in person and if necessary discussing/solving problems in period 1
	Intermediate (4 weeks):
	 Paper-pencil data collection (+ hospitalization and exacerbation rate) Psychophysiological data collection
	Exit (8 weeks):
	 Paper-pencil data collection (+ hospitalization rate, exacerbation rate credibility/expectancy) Psychophysiological data collection Short exit-interview (telephone)

	Period 2 (follow-up)
	Follow-up 1 (4 months):
	 Paper-pencil data collection (+ hospitalization and exacerbation rate) Psychophysiological data collection Chronic stress (collection of hair sample)
	Follow-up 2 (6 months):
	 Paper-pencil data collection (+ hospitalization and exacerbation rate) Psychophysiological data collection Chronic stress (collection of hair sample) Post-monitoring interview
INTERVENTION	Daily short mindfulness exercises delivered via app
	 App provides 4 audio-files of guided mindfulness exercises Length: 10-15 minutes Mindfulness exercises: Body awareness meditation (Body-scan) Sitting meditation: awareness of the heartbeat Sitting meditation: awareness of the body Sitting meditation: awareness of sounds
	Dose: Patients can choose individually between exercises
	Daily practice: instructions to practice at least once each day, either in the morning or the evening (patients choose in the beginning if they prefer meditating in the morning or in the evening)
	Additional practice: additional meditations are possible and encouraged (it is advised to practice when experiencing respiratory problems, feeling distressed, feeling stressed or whenever considered to be beneficial)
CONTROL	Waitlist control group (receiving treatment as usual during the intervention period)
CONDITION	(same collection of psychophysiological, psychological and biological data, except for the intervention-related measures right before and after the intervention)
INCENTIVES	Weekly "checking-in calls"
CONCOMITANT MEDICATION	Allowed (but must be monitored)

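### HADS, a primary outcome, is to be tested by a repeated-measures ANOVA that names no deciding effect and has no baseline covariate

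*Protocol*

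**What the plan says.** The Primary Outcome Variables row lists psychological distress, measured by HADS, alongside feasibility. The Statistical Methodology row states the hypothesis that the intervention lowers distress and then fixes the method: "Groups (intervention vs. waitlist) will be compared regarding subjective variables (e.g. psychological distress" and other variables, by repeated-measures ANOVA. On the tests it says: "These analyses test for main effects of time (within subject factor) and group (between subject factor) as well as their interaction effect". Mediators and moderators follow (age, gender and disease severity are examples), but baseline HADS is not named as a covariate. No section says which of the three effects answers the hypothesis, or at which visit.

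The Measurements row sets the schedule for the questionnaires: "Paper-pencil data collection (baseline, 4 weeks, 8 weeks, 4 months, 6 months". The Patients / Groups row gives 30 patients, 15 per group. Entry depends on HADS: "HADS-A ≥ 8 OR HADS-D ≥ 8 OR HADS total score ≥ 16".

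**The concern.** The main effect of time compares no groups, so the wording on group comparison leaves two candidates: the group main effect and the interaction. They measure different things and can give different answers on the same data.

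If baseline is a level of time, the group main effect averages in a visit at which randomisation makes the true difference zero, so it understates any later effect. The interaction does use baseline, but it asks only whether the group difference varies over the five visits. It does not say in which direction, and it gives no single estimate, although the hypothesis has a direction.

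Neither test yields one baseline-adjusted group difference with a confidence interval. Planners of a later trial would want that figure, and the Executive Summary says: "The results of this study could serve as basis for following large-scale RCTs". With 15 patients per arm, precision is scarce, and baseline HADS is collected anyway.

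**Working it through.** **Plan's own figure.** There is none to reproduce: the protocol gives no alpha, power, effect size, SD or correlation.

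**Inputs from the protocol.** n = 15 per arm; five visits, one of them baseline.

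**Assumptions.** Two-sided 5%, SD 1 at every visit, equal correlation r between visits, complete data, baseline as a level of time. Selection on HADS can lower the correlation with baseline, so r = 0.3 is shown as well.

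**Dilution.** The group main effect estimates the mean difference over five visits: (0 + 4 × 0.8) / 5 = 0.64 SD, which is 4/5 of 0.8.

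**Power for a constant 0.8 SD effect**

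- *Group main effect.* SE = √[(2/n)(1 + 4r)/5], noncentral t with 28 df. At r = 0.5, SE = √(0.1333 × 0.60) = 0.283 and 0.64/0.283 = 2.26, so power is 59%. At r = 0.7, SE = √(0.1333 × 0.76) = 0.318 and the ratio is 2.01, so power is 49%.
- *Interaction.* λ = (n/2) Σ(δₜ − δ̄)² / (1 − r), noncentral F with 4 and 112 df. Σ = 0.64² + 4 × 0.16² = 0.512. At r = 0.5, λ = 7.5 × 0.512/0.5 = 7.68, so power is 56%. At r = 0.7, λ = 12.8, so power is 81%.
- *Baseline-adjusted post-baseline average.* Residual variance = (1 + 3r)/4 − r². At r = 0.5 this is 0.625 − 0.25 = 0.375, so SE ≈ √(0.1333 × 0.375) = 0.224 and 0.8/0.224 = 3.58; simulated power is 92%. At r = 0.7 it is 0.775 − 0.49 = 0.285, so SE ≈ 0.195 and the ratio is 4.10; simulated power is 97%.
- *Baseline-adjusted week 8.* Residual variance = 1 − r². Simulated power is 67% at r = 0.5 and 83% at r = 0.7.

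The adjusted figures come from ANCOVA in 40,000 simulated trials per case. With complete data, the mixed-model average equals ANCOVA of each patient's post-baseline mean.

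**Other effect shapes.** Power (%) as interaction / group main effect / adjusted average / adjusted week 8; effects in SD at the four post-baseline visits:

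| Effect | r = 0.3 | r = 0.5 | r = 0.7 | r = 0.8 |
|---|---|---|---|---|
| Constant 0.8 | 42/72/92/58 | 56/59/92/67 | 81/49/97/83 | 95/46/99/93 |
| Growing 0.2, 0.4, 0.6, 0.8 | 33/36/55/19 | 45/28/56/22 | 69/23/68/31 | 88/21/81/41 |
| Peaked 0.5, 1.0, 0.75, 0.5 | 45/59/82/78 | 60/47/83/85 | 84/39/92/95 | 96/36/97/99 |
| Fading 0.8, 0.8, 0.4, 0 | 51/36/55/58 | 67/28/56/67 | 90/23/68/83 | 98/21/81/93 |

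The adjusted average beats the group main effect in all 16 cases. It is below the interaction in 5: growing at r = 0.7 (by one point) and 0.8, and fading at r = 0.5, 0.7 and 0.8.

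**Precision of the adjusted contrast.** The expected 95% CI half-width at r = 0.5, 0.7 and 0.8 is 0.46, 0.40 and 0.35 SD for the average, and 0.65, 0.54 and 0.45 SD for week 8.

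**If only post-baseline visits entered the ANOVA.** The dilution would vanish, but the interaction would then miss a constant effect and baseline would go unused.

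**The case against.** **It could be left to the SAP.** The deciding contrast and the covariates often are. That would settle the matter if the protocol were silent. But it chooses the model and lists its tests, so an SAP with one baseline-adjusted contrast would depart from the stated method.

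**The ANOVA is a coherent analysis.** This stands. Nothing in the text is false, the interaction is valid, and on the natural reading baseline is already in the model as a level of time. A reader might infer bias from the missing covariate. Under randomisation there is none.

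**The proposed contrast is not best everywhere.** This also stands, as the table shows. The clear loser is the group main effect, which the protocol does not designate as its answer. In addition, the protocol places HADS under both intermediate and long-term effects, and an average over all visits merges the two. The choice between the average and week 8 therefore belongs to the team.

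**It is a 30-patient pilot with feasibility as the other primary outcome.** That limits the weight of the point, but HADS is still a primary outcome with its own hypothesis.

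**Inflated error.** A reader might infer that the false-positive rate is nearly doubled. If either ANOVA effect were allowed to count, it would be 1 − 0.95² = 9.75%, and if any of HADS-A, HADS-D and the total could count as well, 17% to 19% (assuming a subscale correlation of 0.7 to 0.5). The protocol states neither rule, so these figures show what an open choice could cost and do not describe the plan.

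**Waitlist timing.** A reader might also see a contradiction between "provision of mindfulness intervention to waitlist control group after study completion" (Ethics) and "Waitlist control group (receiving treatment as usual during the intervention period" (Control Condition). The two are compatible. Planned duration is 6 months including follow-up, and the second statement is silent on follow-up; it does not say that controls cross over at 8 weeks.

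**Conclusion.** The point holds as one of efficiency and focus. The protocol fixes a method for a primary outcome without saying which effect answers the hypothesis, and makes no use of baseline HADS as a covariate. For a constant effect of 0.8 SD, the baseline-adjusted average has 36 points more power than the interaction and 33 more than the group main effect at r = 0.5 (92 − 56 and 92 − 59). At r = 0.7 the gains are 16 and 48 points (97 − 81 and 97 − 49).

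These sizes rest on assumed effect sizes and correlations, equal correlation between visits and no dropout, none of which the protocol gives. The 4/5 dilution also depends on baseline being a level of time. The documents support neither bias nor an actual error rate of 9.75%. The point should be fixed because the remedy is nearly free, but it does not make the trial invalid.

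**What to change.** For HADS, replace the ANOVA sentence with text along these lines:

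*One named HADS score will be analysed by a linear mixed model (or ANCOVA) of the post-baseline values, with baseline HADS as covariate. The primary result is one between-group contrast, [the average over the post-baseline visits / the difference at week 8], reported with its 95% CI. Differences at other visits and the group-by-visit test are supportive. The main effect of time is not evidence of an intervention effect.*

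The score and the contrast must be fixed before data are seen. If the average over all visits is chosen, confirm in one line that controls stay on the waitlist through 6 months.

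**Cost.** Wording only. No new data are needed, SPSS and R are already named under Data Management, and for the EMA data "multilevel modelling will be used to fit the nested data structure". The mixed model assumes that missing values are missing at random.

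The real price is committing to one contrast:

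- *The average* has less power than the interaction if the effect fades and r is 0.5 or more (56% against 67% at r = 0.5; 68% against 90% at r = 0.7). The same holds if the effect grows late and r is 0.8 (81% against 88%); at r = 0.7 the two are about equal.
- *Week 8* has less power than the interaction if the effect grows late (22% against 45% at r = 0.5), if it fades at r of 0.7 or more (83% against 90% at r = 0.7), and slightly if it is constant at r = 0.8 (93% against 95%). It also falls below the group main effect for a constant effect at r = 0.3 (58% against 72%) and for a growing one at r of 0.5 or less (22% against 28% at r = 0.5).
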